## **4.4 Secondary Outcome Analysis**

***Quality of Life (SIS):*** The SIS total score will be analyzed in a similar manner to primary continuous outcomes. A mixed model with group, time, and group $\times$ time will test for

differences in trajectory. We anticipate improvements in SIS especially in the intervention group if physical and mental health improve. If SIS was only measured at baseline and 6 months (depending on study logistics), then a simple ANCOVA on 6-month SIS (adjusting for baseline SIS) will be done. SIS domain scores can be analyzed descriptively. Because SIS is a secondary endpoint, p-values will be interpreted cautiously.

**Categorical Outcomes:** If we derive any categorical outcomes (e.g., depression remission yes/no at 6 months, or proportion with any improvement in BI by  $>10$  points), these will be compared using chi-square tests or Fisher's exact test between groups. For example, we might define "clinically significant improvement" in PHQ-9 as a drop of  $\geq 5$  points or final PHQ-9  $< 5$ ; we would then compare the fraction meeting that in each group (report risk difference or odds ratio with CI). These analyses are exploratory and will be clearly indicated as such.

**Subgroup Analyses:** We do not have pre-specified subgroup hypotheses, but exploratory subgroup analyses may include looking at whether the treatment effect on depression differs by gender, age group ( $<65$  vs  $\geq 65$ ), or baseline depression severity (PHQ-9 median split). This would involve adding an interaction term between treatment and subgroup in the model. Given limited power, these will be interpreted with caution.

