## 2. Analysis Populations

**Intent-to-Treat (ITT) Population:** The ITT population consists of all participants who were randomized, regardless of whether they completed the intervention or follow-up assessments. Each participant will be analyzed in the group to which they were originally assigned. The ITT population is the primary analysis set for efficacy outcomes, preserving the benefits of randomization.

**Per-Protocol (PP) Population:** The PP population is a subset of ITT including only those participants who completed the study with no major protocol deviations. For the intervention group, “completed the study” is defined as attending the majority of intervention sessions (at least 6 out of 8 MI sessions and at least 5 out of 6 months of rehab visits) and completing the 6-month follow-up assessment. For the control group, it entails completing the 6-month assessment and not adopting outside interventions similar to the study intervention. Major protocol deviations (if any occur, such as ineligibility discovered after randomization or failure to follow key procedures) will be listed and those cases may be excluded from PP analysis. The PP analysis will serve as a sensitivity analysis to see if results are consistent with the ITT analysis.

**Safety Population:** As this study involves minimal-risk behavioral interventions, no separate safety analysis population is defined; any adverse events will be descriptively reported for all enrolled participants.

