### 3. Outcomes and Endpoint Definitions

#### Primary Efficacy Outcomes:

- **Depression Severity:** Change in Patient Health Questionnaire-9 (PHQ-9) score from baseline to follow-ups. The PHQ-9 is a 9-item scale (0–27 range); higher scores indicate worse depressive symptoms. The primary comparison will be the difference in mean PHQ-9 change from baseline to 6 months between groups. Additionally, trajectories over all time points will be considered. We will also examine the proportion of participants in each group achieving remission of depression (PHQ-9 < 5, for example) at 6 months as a supportive outcome.

- **Fatigue Level:** Change in Fatigue Severity Scale (FSS) score (range 9–63, higher = more fatigue). Same approach as PHQ-9: continuous score change and possibly categorization (e.g., FSS  $\geq 36$  indicating significant fatigue) for supplementary analysis.

- **Cognitive Function:** Change in Mini-Mental State Examination (MMSE) score (0–30, higher = better cognitive function). We will consider the mean change and group differences; additionally, the proportion of participants with cognitive impairment (MMSE  $\leq 24$ ) at each time point will be noted.

- **Physical Functional Independence:** Change in Barthel Index (BI) score (0–100, higher = more independent). Primary focus on mean score change at 6 months. Also, we may categorize outcomes (e.g., BI  $\geq 90$  as independent vs <90) for descriptive comparison.

Each of these primary outcomes will be analyzed as a continuous variable using appropriate parametric or nonparametric methods as outlined in Section 4. The primary time horizon for efficacy is the 6-month post-intervention assessment, though intermediate time points will be analyzed to observe trends.

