### ***Missing Data Handling:***

Missing data is expected primarily from dropouts (participants who miss the 6-month assessment, for example). The primary mixed-model analysis (LMM or GEE) can accommodate missing-at-random (MAR) data by using all available observations per participant without imputation. This is our main strategy for ITT analysis – using mixed models inherently includes participants with partial data. However, we will examine the pattern of missingness: if dropout is related to observed characteristics (e.g., those with worse baseline depression are more likely to drop out), the mixed model (assuming MAR conditional on those characteristics) should handle it; if we suspect data are not missing at random, we may perform a sensitivity analysis with imputation.

For sensitivity, we will perform a multiple imputation for missing 6-month outcomes. We will use a multiple imputation by chained equations (MICE) approach including baseline values, group, and available follow-up values to impute missing outcomes. Perhaps 20 imputations will be generated. The primary outcomes will then be analyzed on each imputed dataset and pooled results reported. We may also use a simpler Last Observation Carried Forward (LOCF) as a very conservative scenario (assuming no change after dropout) and re-run primary comparisons to see if conclusions change. The LOCF analysis will not be primary but provides a worst-case bound (especially if the control group has higher dropout, LOCF would bias toward no difference).

Participants who withdraw consent entirely or are lost to follow-up will not contribute post-dropout data; they remain in ITT (with whatever data available up to withdrawal). If a participant dies during the study (which is possible given stroke population), that is a competing risk; we will include them in analysis up until the point of death. If many deaths occur (expected to be low), we could consider a composite outcome or survival analysis for mortality, but given sample size we will likely just report any deaths separately.

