#### **4.7 Assumption Checks**

**Normality and Homogeneity:** We will use Shapiro-Wilk tests and Q-Q plot inspections for normality of residuals for key models. If PHQ-9 or other scores show significant skew, we may confirm results with nonparametric tests (e.g., Wilcoxon rank-sum for endpoint differences, or a rank-based ANOVA). Similarly, Levene's test will be used to assess equality of variances between groups for t-test/ANOVA assumptions. The repeated measures ANOVA requires sphericity; we will apply Mauchly's test for sphericity. If sphericity is violated, the Greenhouse-Geisser correction will be applied to F-tests (as already anticipated). The linear mixed model approach does not require sphericity, which is one reason we favor it primarily.

**Independence:** Given randomization, independence of observations across participants is expected. We will ensure no clustering effects (since single center, no cluster-randomization, except repeated measures within subjects which is handled by paired models).

**Model Fit:** For mixed models, we will check that model residuals vs fitted plots show no major deviations (e.g., heteroscedasticity). If necessary, we might try a transformation of an outcome (e.g., log-transform FSS if very skewed). For binary outcomes (if any logistic regression is used in subgroup or supplementary analyses), we will check for small sample issues (Firth's correction if cell counts are small) and overfitting.

**Multiplicity:** We acknowledge multiple outcomes are being tested (four primary scales). Our focus is on the collective evidence across these outcomes rather than any single hypothesis. Thus, we are not formally adjusting  $\alpha$  for multiple comparisons in the primary domain; however, we will interpret the pattern of results (e.g., if all four move in the favorable direction with several significant, that strengthens conclusions). Secondary outcomes and subgroup analyses will be considered exploratory.

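### The supportive 6-month remission comparison is planned without baseline PHQ-9, which gives up power that data already collected would recover

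*SAP*

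**What the plan says.** SAP section 3 places remission inside the PHQ-9 entry. The proportion with PHQ-9 below 5, a cut-off offered as an example, is examined "at 6 months as a supportive outcome". SAP 4.4 (Categorical Outcomes) supplies the method for binary outcomes: "these will be compared using chi-square tests" or Fisher's exact test, with a risk difference or odds ratio and its interval. No covariate is mentioned. The same paragraph adds "These analyses are exploratory and will be clearly indicated as such".

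Elsewhere the SAP does adjust for baseline. The endpoint ANCOVA in 4.3 uses the baseline score of each scale, and so does the fallback analysis of the Stroke Impact Scale in 4.4. Logistic regression appears only in 4.7, as something that might be used in subgroup or supplementary work.

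On missing data, SAP 2 states that "The ITT population is the primary analysis set for efficacy outcomes". SAP 4.3 plans multiple imputation of missing month-6 outcomes by chained equations (MICE) and continues "The primary outcomes will then be analyzed on each imputed dataset and pooled results reported". No sentence says how a patient with unknown month-6 remission status is counted.

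**The concern.** Remission is a threshold on a month-6 score that is likely to depend on where the patient started. A two-by-two table ignores that. The eligibility criteria in the protocol make this matter more: they set no lower limit on PHQ-9, so some patients may already be below 5 at entry. Such a patient counts as remitted simply by staying there. With 46 per arm, a chance imbalance in their number passes straight into the unadjusted risk difference.

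At stake are precision and interpretability. A remission rate is easy to quote, and this one could look weaker than, or at odds with, the mixed model and ANCOVA on the same scale merely because it leaves out the baseline score. A secondary matter is that the mixed model's use of partial data does not carry over to a chi-square test, which needs a month-6 status for every patient it counts.

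**Working it through.** **The plan's own figure.** Inputs from the protocol's sample-size section: difference 3.43, SD 5.5, two-sided alpha 0.05, power 0.80.

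n per arm = 2 × (1.960 + 0.842)² × 5.5² / 3.43² = 40.4, so 41. A t-test calculation gives 42. The stated 43 is reproduced to within 2 patients. No power is stated for any binary outcome.

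**Assumptions not in the documents.** Baseline mean PHQ-9, the fall in controls, and the baseline-to-month-6 correlation r (0.3, 0.5, 0.7).

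**Method.** Simulated PHQ-9 scores were rounded and limited to 0–27, with remission defined as a month-6 score below 5 and 46 patients per arm. The uncorrected chi-square test was compared with the likelihood-ratio test for arm in a logistic regression on arm and baseline PHQ-9.

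**Setting A: 5.5 taken as the SD of the score.** Baseline mean 10, common fall 2 points, 3,000 trials per row. Remission is 26% against 49%.

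| r | chi-square | adjusted | gain (points) |
|---|---|---|---|
| 0.3 | 63% | 67% | 4 |
| 0.5 | 64% | 73% | 9 |
| 0.7 | 65% | 82% | 17 |

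**Setting B: 5.5 taken as the SD of change, as the protocol words it.** The score SD is then 5.5/√(2(1 − r)), which is 4.65, 5.5 and 7.1. Control fall 1 point, 6,000 trials per row.

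| r | baseline mean | remission, control vs intervention | chi-square | adjusted | gain (points) |
|---|---|---|---|---|---|
| 0.3 | 8 | 30% vs 58% | 78.5% | 82.0% | 3.5 |
| 0.3 | 11 | 12% vs 33% | 68.6% | 71.7% | 3.1 |
| 0.5 | 8 | 32% vs 57% | 64.4% | 73.4% | 9.0 |
| 0.5 | 11 | 16% vs 35% | 57.1% | 65.5% | 8.4 |
| 0.7 | 8 | 36% vs 55% | 44.0% | 60.9% | 16.9 |
| 0.7 | 11 | 22% vs 39% | 42.0% | 56.1% | 14.1 |

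Repeat runs gave the same picture. At 43 per arm in setting B the gains are 2.6–2.7, 6.6–7.6 and 13.6–16.3 points. Overall the ranges are about 3–4, 7–10 and 14–18 points.

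**Type I error for remission (no effect, r = 0.5 and 0.7).** Chi-square 5.0–5.1%, adjusted 5.6–5.7%. A little of the gain is therefore small-sample anticonservatism, but not most of it.

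**Already below the threshold at entry.** With baseline mean 10 and SD 5.5, a rounded score below 5 has probability Φ((4.5 − 10)/5.5) = Φ(−1.0), about 16%.

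**Change-based responder rule.** For a PHQ-9 drop of at least 5 or a final score below 5, adjustment gains only 0.4 to 5.6 points in setting B.

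**Barthel example.** The scale maximum is 100, so the largest gain from a baseline of 90 is 10, which is not more than 10. Anyone starting at 90 or above fails in either arm. If a share s starts there, the risk difference is (1 − s) times that among the other patients.

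**The case against.** The strongest reply is that nothing confirmatory rests on this test. SAP 4.4 is conditional and exploratory, SAP 3 calls remission supportive, and the continuous PHQ-9 result comes from a mixed model backed by a baseline-adjusted ANCOVA. That stands, and it limits the severity. The size of the loss also depends on quantities the documents do not give; at a correlation of 0.3 it is small.

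Three stronger readings are tempting but not supported:

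- **A departure from ITT.** A reader might infer that the binary tests are restricted to patients seen at month 6. The SAP does not say so. It makes ITT the main set and imputes missing month-6 outcomes. Since remission sits under PHQ-9, a primary outcome, it could be derived from the imputed scores. What is missing is a rule, although complete cases are the likely default. The effect also looks modest. With assumed dropout of 17% in controls (related to baseline) and 13% at random in the intervention arm, the risk difference moves from 23.5 to 21.3 points, against a standard error of √(0.26×0.74/46 + 0.49×0.51/46), about 10 points. The protocol's 46 against 43 implies only 3/46 = 6.5% dropout.
- **The same power loss for responder rules.** A PHQ-9 drop of 5 or a Barthel gain already uses the baseline score, and the computed gain for the PHQ-9 composite is small.
- **The same faults in the rank test.** "Wilcoxon rank-sum for endpoint differences" in SAP 4.7 is an optional confirmation offered beside a rank-based ANOVA, and the endpoint analysis in 4.3 includes change scores, so the rank test may use baseline too.

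**Conclusion.** The point holds for remission, as a minor one. The planned test is unadjusted, and the covariate it omits is collected and already used for the same scale elsewhere in the SAP. Under the protocol's effect and SD the cost is about 3–4, 7–10 or 14–18 points of power at assumed correlations of 0.3, 0.5 or 0.7. The direction was the same in every setting tried; the size rests on the assumed correlation, baseline mean and control change. The absence of a rule for unknown month-6 status is a gap to fill, not evidence of a completers analysis. The Barthel ceiling is plain arithmetic, but it concerns only the example "proportion with any improvement in BI by" more than 10 points.

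**What to change.** In SAP 4.4, estimate remission by logistic regression on arm and baseline PHQ-9. Report the standardised (marginal) risk difference with a confidence interval, and keep chi-square or Fisher as description. The bootstrap already planned for effect sizes can supply the interval.

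Two smaller additions:

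- State the denominator, and derive remission from PHQ-9 within each planned MICE dataset before pooling. Reconcile SAP 4.3, which plans imputation as a sensitivity analysis without a trigger, with SAP 4.6, which starts it only above 10% missing.
- If the Barthel gain of more than 10 is used, restrict it to patients with baseline below 90. Counting anyone who reaches 100 as a success would not cure the problem, because a patient who starts and stays at 100 would become a fixed success.

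The cost is SAP wording and a few lines of code on data already collected. There are two small downsides. The odds ratio becomes conditional on baseline, which is why the standardised risk difference should lead. The adjusted test is slightly anticonservative at this sample size (5.6–5.7% in the null runs); the Firth correction already named in SAP 4.7 is available if cells are small.

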- **6-Month Follow-up (Month 6, end of study):** At the end of the 6-month study period, all participants undergo the final evaluation. The same battery of outcome measures (PHQ-9, FSS, MMSE, Barthel Index, SIS) is administered, and the **final fNIRS** measurement is conducted. The 6-month outcomes represent the primary endpoint for evaluating intervention effectiveness. By this time, the intervention group has concluded all activities (the last home visit by the physical therapist typically occurs around month 5 or 6 with the monthly schedule). We document any post-study referrals or ongoing care plans for both groups. After completing the 6-month assessment, participants are thanked and exit the study. Those in the control group are offered an opportunity to receive the intervention program after study completion, if appropriate, as an ethical consideration.

Sample Size and Justification

The sample size was determined based on detecting a clinically meaningful difference in depression outcomes between the two groups at 6 months. Using a two-sample comparison of mean change in PHQ-9 scores (intervention vs control), we assumed a difference in mean PHQ-9 reduction of approximately 3.43 points with a standard deviation of about 5.5, based on prior research on post-stroke depression interventions [27]. With a two-sided $\alpha=0.05$ and power (1– β) of 0.80, the estimated minimum sample required was 43 patients per group (calculated via the formula for comparing two means). We planned to enroll 46 patients in each group (total N=92) to account for potential drop-outs and ensure adequate power. This sample size also offers >80% power to detect medium-to-large effects on secondary continuous outcomes like FSS and Barthel Index, given similar variance assumptions. The actual achieved sample size was 92, which meets these targets. No interim analyses for efficacy were planned (due to the relatively short intervention duration and moderate sample size), so the full sample contributes to the final analysis.

Randomization, Allocation Concealment, and Blinding

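### The optional baseline-severity subgroup analysis would split PHQ-9 at the median; a continuous interaction in the 6-month ANCOVA would use the data better

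*SAP*

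**What the plan says.** The subgroup paragraph of SAP 4.4 opens: "We do not have pre-specified subgroup hypotheses, but exploratory subgroup analyses may include" three factors for the effect on depression. These are gender, age cut at 65, and "baseline depression severity (PHQ-9 median split". The method is stated: "This would involve adding an interaction term between treatment and subgroup in the model". The model meant is not named. The paragraph ends: "Given limited power, these will be interpreted with caution". SAP 4.7 repeats the status: "Secondary outcomes and subgroup analyses will be considered exploratory".

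Two models in SAP 4.3 could carry the interaction. The main one is a linear mixed model in which baseline is one of four outcome time points and the treatment effect is the group-by-time term at 6 months. The supportive one is an ANCOVA of the 6-month score with the baseline score as covariate. Neither document plans an interaction of treatment with baseline PHQ-9 as a continuous score, and neither reports the mean, SD or shape of baseline PHQ-9.

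**The concern.** Baseline severity is a natural candidate modifier in this trial. The protocol's eligibility criteria set no minimum PHQ-9 score and the scale stops at 0, so a patient who enters with a score of 3 or less cannot fall by the 3.43 points used in the sample size. Some dependence of the effect on baseline is therefore plausible, and it may well be graded.

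A two-level split shows a graded pattern poorly. It treats all patients within a half as alike and patients just either side of the cut as different. The cut is known only once the data are in, and it need not match the PHQ-9 thresholds that the SAP uses elsewhere: below 5 for remission (SAP 3) and 10 or more for depression status (SAP 4.5). PHQ-9 is an integer score, so ties at the median are likely, and the SAP does not say on which side they fall.

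What is at stake is the efficiency and readability of one exploratory analysis.

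**Working it through.** **Inputs from the documents.** The protocol's sample size section assumes "a difference in mean PHQ-9 reduction of approximately 3.43 points with a standard deviation of about 5.5", two-sided alpha 0.05 and power 0.80. It states that "the estimated minimum sample required was 43 patients per group" and that 46 per group (92 in total) were to be enrolled, with 1:1 allocation. PHQ-9 runs from 0 to 27.

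**Assumptions, not in the documents.** The shape of baseline PHQ-9, the form of the interaction and its slope.

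**1. The plan's own figure.** n per group = 2 × [5.5 × (1.960 + 0.842) / 3.43]² = 40.4, so 41. The t-test version gives 41.3, so 42. The stated 43 is within two patients and counts as reproduced. The documents give no power or efficiency figure for the subgroup analysis.

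**2. Efficiency of the split.** With 1:1 randomisation and a truly linear interaction, the efficiency of the split relative to the continuous score is the squared correlation between the score and its above-median indicator. For a normal score this is 2/π = 0.637.
- Loss: 1 − 0.637 = 0.363, or 36%.
- Equivalent sample: 92 × 0.637 = 59 patients with complete data.
- Sample-size factor: π/2 = 1.57.

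**3. Other assumed shapes.** Simulated scores, with ties placed on either side of the cut:

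| Assumed baseline PHQ-9 | Loss |
|---|---|
| Uniform | 25% |
| Normal, rounded and bounded to 0–27 (mean 5 to 12, SD 5.5 before bounding) | 31–35% |
| Normal | 36% |
| Right-skewed (gamma-type, mean about 4.5 to 8.5) | 37–55% |

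Right skew is plausible because entry needs no minimum score and psychiatric illness before the stroke is excluded. Tie placement can matter: in the most skewed case the loss is 46% with ties in the low half and 55% with ties in the high half.

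**4. Simulated power of the interaction test.** N = 92, residual SD 5.5, linear interaction:

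| Slope (PHQ-9 points per baseline point) | Normal: continuous / split | Skewed: continuous / split |
|---|---|---|
| 0.3 | 29% / 20% | 22% / 16% |
| 0.6 | 78% / 57% | 69% / 47% |

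**5. How far the change helps.** Take four cells of 23 and SD 5.5.
- SE of the split interaction = 5.5 × √(4/23) = 2.29.
- Difference between halves detectable with 80% power = 2.29 × 2.80 = 6.4 points.
- Power for a difference between halves of 3.43: 3.43 / 2.29 = 1.50, and Φ(1.50 − 1.96) = about 32%.
- With the full gain of the continuous term: 1.50 / √0.637 = 1.87, and Φ(1.87 − 1.96) = about 47%.

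**The case against.** The strongest reply is that the SAP has already dealt with the main risks. The analysis is optional, no hypothesis is attached to it, it uses an interaction term rather than separate tests within subgroups, and the low power is admitted. All of that stands, and it is why this is a minor point. A reader might infer that a planned test, or the trial's conclusion on depression, is weakened. The wording of SAP 4.4 and 4.7 does not support that.

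The split also has some merit. It needs no linearity assumption, and it limits the influence of a few high scorers on a bounded scale. If the effect really changed in a step at the cut, the calculated loss would not apply. It would be wrong to say the split brings no benefit.

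Two further readings go too far. One is that this is the weakest analysis in the plan. The documents give no power for any subgroup or fNIRS analysis, and a median split gives near-equal halves, whereas gender or age at 65 may divide the sample unevenly. The other is that the same criticism covers age. The cut at 65 is fixed in advance, so it is not data-dependent, and 2/π applies to a median split of a normal variable, not to that cut.

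What survives is that, where effect modification is graded, the stated method discards information in an analysis that has little to spare, and a better method costs almost nothing.

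**Conclusion.** The point holds as a minor improvement. If baseline PHQ-9 is near normal and the interaction is linear, the median split loses about 36% of the information on that interaction, with 25% to 55% across the shapes tried. A reader might take one third as a known property of this trial. It is not, because the documents report no baseline distribution and offer no evidence of linearity. The equivalence of 92 patients to 59 also assumes complete 6-month data, and SAP 4.3 expects dropouts.

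Nor should anyone conclude that a continuous term rescues the analysis. For an interaction as large as the assumed main effect, power would rise only from about 32% to about 47%. The analysis stays exploratory and of limited power, and no primary conclusion changes.

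**What to change.** In SAP 4.4, replace the median-split test with a treatment-by-continuous-baseline-PHQ-9 product term in the 6-month PHQ-9 ANCOVA of SAP 4.3. That model already contains baseline PHQ-9, so one term is added. Include a simple check for non-linearity. Report the estimated treatment effect with its 95% CI at fixed scores within the observed range, such as the SAP's own thresholds of 5 and 10. Keep the median split for descriptive tables only, and state where ties go.

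The SAP should name the model. In the mixed model, baseline PHQ-9 is itself an outcome time point and the treatment effect is already a group-by-time term. Effect modification there would need a group-by-time-by-severity term, with the same measurement on both sides of the model. The ANCOVA avoids this.

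Age may also be modelled as continuous, as a separate choice that does not rest on the figures above.

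The cost is a few lines of SAP wording, a linearity assumption that needs checking, and possible leverage from a few high baseline scores.
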